- ⑩ Adverse effects, including possible alteration of ocular structure and function, Cas9-specific immunoreaction or off-target editing of CRISPR in the bloodstream. Postoperative B-scan ultrasonography, time-domain OCT, spectral-domain OCT, and electroretinography (ERG) will be used to evaluate ocular status. ELISA and Whole-genome sequencing (WGS) will be conducted on the blood samples collected at 3-month and 6-month visit, respectively.

Table of Contents

1. Introduction	30
1.1 Study Objects.....	30
1.2 Backgrounds of HELP.....	30
2. Eligibility Criteria	30
2.1 Inclusion Criteria.....	30
2.2 Exclusion Criteria.....	31
3. Study Implementation	32
3.1 Study Design.....	32
3.2 Preparation of HELP Formulation.....	33
3.3 Corneal Transplant and HELP Administration.....	34
3.4 Post-operation Management.....	35
4. CRISPR/Cas9 Therapy Interruption	36
5. Quality Control	36
5.1 Quality Control and Quality Assurance.....	36
5.2 Monitoring.....	36
6. Data Collection and Evaluation	37
7. Statistical Considerations	38
8. Adverse Event Reporting	38
8.1 Adverse Event.....	38
8.2 Serious Adverse Event.....	38
8.3 Recording and Reporting.....	39
9. Record Form & Retention	40
10. Ethics	40

10.1	Ethical Conduct of the Study.....	40
10.2	Patient Information and Consent.....	40
11.	Reference.....	42

1. Introduction

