3.1 Study Design

The enrollment of participants initiates relevant processes immediately. After the completion of preoperative examinations, participants with corneal perforation will be arranged for transplantation as soon as possible. During the usual procedure of the surgery, CRISPR/Cas9 mRNA formulation in the form of HELP will be administrated for the treatment of refractory HSK. The hospital observations of participants will persist for 7 days. The postoperative recovery condition, HSV-1 testing outcome, adverse effects of the participants will be examined at every follow-up time. After their hospital discharge on 7th day, follow-up will be conducted on 1 month, 2 months, 3 months, 6 months and 12 months after the surgery. The basic information is shown in the Table 1. below.

Table 1. Basic Information of Our Clinical Study

Item	Content
Study Type	Interventional (Clinical Trial)
Estimated Enrollment	3-6 participants
Allocation	N/A
Intervention Model	Single Group Assignment
Intervention Model Description	Single group target value: Since there is no similar products approved on the market or similar comparative treatment methods, the single group target value method is adopted
Masking	None (Open Label)
Primary Purpose	Treatment
Actual Study Start Date	November 4, 2020
Estimated Primary Completion Date	November 2021
Estimated Study Completion Date	May 2022

In this study, each participant diagnosed with terminal refractory HSK will undergo HELP injection during the normal procedure of penetrating keratoplasty (PK). Before the surgery, they will receive conventional topical or systemic antiviral treatment. During the operation, single dose CRISPR/Cas9 mRNA formulation in the form of HELP will be injected into the recipient graft bed. Then the participants will no longer receive any forms of antiviral treatment unless occurs an uncontrollable virus recurrence, when the conventional antiviral therapy continues. At follow-up visits, participants will undergo a series of examinations, including best-corrected visual acuity, intraocular pressure, photograph of anterior segment, postoperative B-scan ultrasonography, time-domain optical coherence tomography (OCT), spectral-domain OCT, electroretinography (ERG), ELISA of blood samples, deep sequencing of corneal epithelial cells, HSV-1 testing and potential adverse events.

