5.2 Monitoring

The potential audits and inspections, including source data verification, must be accepted by representatives designated by the Protocol Chair. Through these audits and inspections, monitors will examine whether the medical activities and documents related to this study were following the protocol, institutional regulation, and any applicable policy requirements. Monitoring will start at the first time of participant registration and will continue during the entire protocol performance.

6. Data Collection and Evaluation

Unless noted, the procedures for all patients must be identical. Any AE/SAE will be documented and reported throughout the study. The period of data collection will be divided into three sections, including pre-study screening, study procedure and post-study follow-up. Screening procedures for baseline data will be taken 3~14 days prior to CRISPR/Cas9 gene editing treatment. An, and institutional Review Board (IRB) approved informed consent document (ICD), must be signed and dated before any specific procedures are done. Results from standard clinical assessments or laboratory tests, prior to the date of informed consent but within the allowed time restraint for screening procedures, can be used for determining the patient's eligibility. The patient's source documents must clearly document the use of pre-consent results. A screening will contain the following items:

- ⑩ Sign form of informed consent
- ⑩ Disease history and prior treatment
- ⑩ Complete ophthalmic examinations
- ⑩ Vital signs
- ⑩ Laboratory evaluation
- ⑩ Other necessary items depending on specific situations

During the study period, each patient will receive corresponding treatment according to the protocol, which was elaborated in the “Study Implementation” section. After the procedure, all the patients will be scheduled a follow-up for 360 days or more, the patients will be followed up 7 ± 2 days, 30 ± 7 days, 60 ± 10 days 90 ± 14 days, 180 ± 21 and 360 ± 31 days after treatment, where their post-treatment status will be carefully evaluated.

7. Statistical Considerations

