This is an open-label, single-arm clinical study. The investigators conducted this research to evaluate the safety and efficacy of HSV-1-targeting CRISPR formulation HELP for in vivo treatment of refractory HSK patients. In this study, participants will receive a single dose of HELP formulation by intrastromal injection during the penetrating keratoplasty for acute corneal perforation. At each follow-up point, a series of safety and effectiveness evaluations will be performed.

The primary endpoint, HSV-1 in tear swabs will be evaluated at various test points according to the data collection plan, as summarized by simple descriptive summary. For safety evaluations, clinical examinations (slit-lamp examination, measurement of best-corrected visual acuity, intraocular pressure, B-scan ultrasonography, the time-domain OCT, the spectral-domain OCT, and the ERG) will be presented as simple descriptive statistics in the form of pictures, line charts or summarized tables. Deep sequencing of the corneal epithelial cells (acquired by corneal wipes) will also be reported as descriptively summarized tables. Blood ELISA will be reported graphically with the aid of the Student's test. Other laboratory and imaging correlative studies will also be reported descriptively and graphically.

8. Adverse Event Reporting

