2.1	Adjust the inclusion criteria	Patients with refractory keratitis caused by herpes virus type I who has acute corneal perforation or had at least one time failed corneal transplant due to the virus relapse.

Original and Current Statistical Analysis Plan

Statistical Analysis Plan

This is an open-label, single-arm, non-randomized interventional trial. The investigators conducted this research to evaluate the safety and efficacy of HSV-1-targeting CRISPR formulation HELP (BD111) for in vivo treatment of refractory HSK patients. In this study, participants will receive a single dose of HELP formulation by intrastromal injection during the penetrating keratoplasty for acute corneal perforation. At each follow-up point, a series of safety and effectiveness evaluations will be performed.

The primary endpoint, HSV-1 in tear swabs will be evaluated at various test points according to the data collection plan, as summarized by simple descriptive summary. For safety evaluations, clinical examinations (slit-lamp examination, measurement of best-corrected visual acuity, intraocular pressure, B-scan ultrasonography, the time-domain OCT, the spectral-domain OCT, and the ERG) will be presented as simple descriptive statistics in the form of pictures, line charts or summarized tables. Deep sequencing of the corneal epithelial cells (acquired by corneal wipes) will also be reported as descriptively summarized tables. Blood ELISA will be reported graphically with the aid of the Student's test. Other laboratory and imaging correlative studies will also be reported descriptively and graphically. Data were analysed using GraphPad Prism 8 and presented as mean \pm SEM in all experiments (n=3). Unpaired two-tailed Student's t-tests were performed to determine the P values (95% confidence interval). n.s., non-significant.

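### The SAP prescribes unpaired t-tests and mean ± SEM (n=3) for a single-arm trial of 3-6 participants, but names no independent second group and does not define n

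*Combined protocol and SAP*

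**What the plan says.** The SAP (Original and Current Statistical Analysis Plan) opens: "This is an open-label, single-arm, non-randomized interventional trial". The current protocol's Description and Table 1 plan 3-6 participants.

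The SAP and section 7 of the current protocol both state: "Blood ELISA will be reported graphically with the aid of the Student's test". No other measure is explicitly tied to a test, and HSV-1 in tear swabs, the primary endpoint, is to be summarised descriptively.

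The SAP alone then adds that data are presented as mean ± "SEM in all experiments (n=3"), followed by "Unpaired two-tailed Student's t-tests were performed to determine the P values (95% confidence interval") and an expansion of the abbreviation n.s. Neither document names a second group, says which visits would be compared, or says whether n counts participants, samples or assay replicates.

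The current protocol's secondary outcomes list, among adverse effects, "Cas9-specific immunoreaction or off-target editing of CRISPR in the bloodstream". ELISA and whole-genome sequencing "will be conducted on the blood samples collected at 3-month and 6-month visit, respectively". That ELISA is the assay for the Cas9 immune response is an inference, because the list does not assign an assay to each effect.

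**The concern.** An unpaired t-test needs two independent sets of independent observations. A one-arm trial does not supply them unless a control is brought in from outside, and none is named. Three situations could lie behind the SAP sentence, and they behave differently:

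1. **Visits of the same participants are compared.** The observations are paired, and the independence assumption fails.
2. **n=3 counts assay replicates.** The SEM and P value then reflect assay error only and say nothing about variation between samples or participants.
3. **An independent control group is used.** The test can support inference about participants, but the group is missing from the plan.

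At stake is how a blood safety result for a gene-editing product is read. A P value, or an n.s. label, would be attached to it without the reader knowing which of these was done. SEM bars at n=3 would also make the result look more precise than it is.

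**Working it through.** **Inputs.** One arm (SAP); 3-6 participants (current protocol); n=3, mean ± SEM, unpaired, two-tailed (SAP). Alpha is not stated; 0.05 two-sided is assumed from the SAP's mention of 95%. The documents give no correlation, SD ratio or expected ELISA shift, so those below are assumed ranges and the results are scenarios, not this trial's error rates. The plan has no sample-size or power figure to reproduce, and n=3 has no derivation. Normal data are assumed throughout.

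**SEM bars.** Coverage of mean ± 1 SEM is P(|t| < 1) on n − 1 df.
- n=3: P(|t₂| < 1) = 1/√3 = 57.7%; the 95% interval is ± 4.30 SEM.
- n=6: P(|t₅| < 1) = 63.7%; the 95% interval is ± 2.57 SEM.

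**Situation 1, same participants at two visits.** With common SD σ and correlation ρ, the difference in means has variance 2σ²(1 − ρ)/n, while the unpaired test assumes 2σ²/n. Simulated rejection with no true change (at least 1,000,000 draws):

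| ρ | n=3 | n=6 |
|---|---|---|
| −0.5 | 9.5% | 10.5% |
| 0 | 5.0% | 5.0% |
| 0.5 | 2.1% | 1.2% |
| 0.8 | 0.75% | 0.2% |

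The test is conservative if the correlation is positive and over-rejects if it is negative.

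**Situation 2, three replicates of one sample against three of another.** Let r be sample-to-sample SD divided by assay SD. The difference in means has variance proportional to r² + 1/3, and the test assumes 1/3, a ratio of 1 + 3r². With critical value 2.776 on 4 df, rejection when participants do not truly differ on average is 2 × P(T₄ > 2.776/√(1 + 3r²)):
- r = 0.5: 2.776/√1.75 = 2.10, giving 10%.
- r = 1: 2.776/√4 = 1.39, giving 24%.
- r = 2: 2.776/√13 = 0.77, giving 48%.

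If the question is only whether those two samples differ in concentration, r plays no part and the test holds 5%.

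**Situation 3, independent control.** The size is 5% by construction, given normality and equal variances, which n=3 cannot check.

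**Width of a paired analysis.** The half-width of the 95% interval, in SDs of change, is t/√n: 4.303/√3 = 2.48 at n=3 and 2.571/√6 = 1.05 at n=6.

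**The case against.** Several points on the other side stand.

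- **Replicates can be tested validly for a narrower question.** Triplicates with independent assay error do compare two specific samples at the nominal level. The false-rejection figures arise only when the result is carried over to participants, which is the interpretation a clinical safety measure invites.
- **Low power cannot be asserted outright.** A reader might infer that any test at n=3 is hopeless. For 3 against 3 independent participants, power is 16% at a 1-SD shift, 46% at 2 SD, 78% at 3 SD and 95% at 4 SD. The documents give no expected shift, so whether power is low is unknown.
- **Pairing is not always more powerful at n=3.** It leaves 2 df. At a 3-SD shift, unpaired against paired power is 78% v 51% at ρ = 0, 82% v 75% at ρ = 0.5 and 83% v 96% at ρ = 0.8. The case for pairing is that it matches the data and gives correct coverage.
- **The ELISA timing is not shown to conflict.** A reader might see a contradiction between the 3-month visit in the outcome list and section 3.1, which includes "ELISA of blood samples, deep sequencing of corneal epithelial cells, HSV-1 testing and potential adverse events" among follow-up examinations. Section 3.1 does not say that every examination happens at every visit, so the two are compatible. Screening in section 6 names only "Laboratory evaluation" and other necessary items, so a baseline ELISA is unstated, not excluded.
- **The plan does not say that n.s. means no immune response.** It only expands the abbreviation. Likewise, bars labelled as SEM are not presented as 95% intervals. The risk in both cases is misreading.

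None of this supplies a second group or defines n. If the closing sentences are standard laboratory wording, they do not describe this trial's analysis and should be replaced.

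**Conclusion.** The point holds. The SAP prescribes an unpaired test for a design that contains no independent second group, with an undefined n. An unpaired test supports inference about participants only against an independent group, and none is named.

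The size depends on what was meant. At an assumed 5% level and n=3, the true error rate is about 2% for repeat visits at correlation 0.5. It is 10-48% for replicates read as participants, at SD ratios of 0.5 to 2. It is 5% against a genuine independent control. A reader might infer that the plan inflates false positives in general. The documents do not support that, because the direction differs by situation and, for repeat visits, by the sign of the correlation. The SEM coverage of 57.7% at n=3 needs only independent normal data; if n counts replicates, it refers to that sample's concentration and not to a participant mean.

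The consequence is confined to interpreting the ELISA safety result. The primary endpoint is descriptive, no decision rule uses the P value, and adverse events are recorded individually in any case. A reader should not infer that the efficacy conclusion rests on this test.

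**What to change.** Replace the closing SAP sentences with:

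> Blood ELISA values will be shown for each participant at each sampled visit, after averaging assay replicates within participant; n is the number of participants sampled. Where an earlier sample exists, within-participant change will be reported as a paired mean difference with a 95% t-interval (df = participants − 1). Otherwise values will be descriptive, with no P value. An unpaired test will be used only against an independent control group named here with its source and size. Individual points or 95% intervals will replace SEM bars. A non-significant result will not be read as absence of an immune response.

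The cost is a few sentences and the re-plotting of small data sets. The intervals will be very wide, about ± 2.5 SDs of change at n=3 and ± 1.05 at n=6, and may be of little use at the lower end of enrolment. For some shifts and correlations, the paired test will have less power at n=3 than the unpaired one. If no earlier blood sample was taken, there may be no formal test at all, only individual values.
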